## 6. Risks

Completion of the questionnaires and administration of EPO are the only 2 procedures from this protocol that are outside of the realm of standard of care for the radical prostatectomy patient. All of the questionnaires will be completed by the participants pre-operatively allowing them time to assess if this activity is something they are willing to complete 4 times post-operatively. If the questionnaires cause any type of discomfort or uneasiness at that time or any time during the study, the participant can decide to end their involvement with the protocol.

Date: March 16, 2017

Principal Investigator: [name].

Application Number: IRB00048594

Possible adverse effects of EPO include pain, redness or swelling at the injection site, headache, joint or muscle pain, nausea, vomiting, indigestion, stomach pain, diarrhea, constipation, runny nose, sneezing, difficulty falling or staying asleep, excessive sweating, or rash.

Serious adverse effects associated with EPO (extremely rare) include anaphylaxis, cerebrovascular accident, deep venous thrombosis, hypertension, acute left ventricular failure, myocardial infarction, pulmonary embolism, seizure, thrombotic disorder, hemoptysis, chronic cough, production of antibodies causing severe anemia, transient ischemic attack, aphasia, confusion and death.

The occurrence of any serious adverse effects will end the patient's participation in the study and halt enrollment in the study to determine the safety of continuing the study. Each and every possible adverse effect of EPO will be investigated and treated individually to minimize the participant's discomfort. The safety of having the individual complete the study will also be assessed on an individual basis. At any time the participant can decide to terminate his participation in the study and no penalty or loss of benefits to which they are entitled.

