### **2. Study Procedures**

The study design will be a single center, randomized, double-blind, placebo-controlled, 2-arm study, comparing the effects of recombinant human erythropoietin vs. saline placebo on erectile function recovery in men after bilateral nerve-sparing radical prostatectomy. The dosing regimen: a three (3) day

Date: March 16, 2017

Principal Investigator: [name].

Application Number: IRB00048594

intensive treatment of 300 units/kg subcutaneously and then 33,000 units intravenously was used in a previously reported clinical trial of erythropoietin for acute stroke. Similarly, the dosing regimen for this clinical trial will be ~300 units/kg subcutaneously for a 3-day treatment plan – the exact dose will be 20,000 units given as a subcutaneous treatment on the day prior to surgery and 20,000 units given subcutaneously on the day of and day after surgery.

The sample size will be 25 patients randomized to each study arm (50 patients total). Study procedures will involve screening and informed consent after initial consultation, baseline evaluation including medical clearance and completion of validated questionnaires, randomization, therapy (preoperative day dosing, dosing 0-2 hours prior to surgery, postoperative day 1 dosing), follow-up with blood draw for hematocrit and hemoglobin levels at 2 weeks post-op and then follow-up (completion of efficacy questionnaires at 3, 6, 9 and 12 months postoperatively). Assessment tools will consist of the following questionnaires which will be administered online using a REDCap site hosted by the Data Informatics Services Core within the Johns Hopkins Biostatistics Center or via mail per patient preference: IIEF questionnaire, the Quality of Erection Questionnaire (SEQ), and the version of the Expanded Prostate Cancer Index Composite (EPIC) that combines the Short Form Health Survey (SF-12) and AUA Symptom Index (AUA-SI). Standard practice associated with surgery, blood transfusion and postoperative laboratory testing will be performed. Patients will be prescribed a phosphodiesterase type 5 inhibitor (sildenafil, tadalafil or vardenafil) at 1 month following surgery to be used as conventional “on-demand” therapy. Adverse event monitoring will be performed. PSA monitoring is recommended at 3 and 12 months with the definition for biochemical recurrence set a PSA of 0.2ng/mL (rising from an undetectable level after surgery).

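### Section 6 ends a man's participation after any serious adverse effect; because dosing stops on post-operative day 1, the rule read literally cuts off his remaining IIEF questionnaires rather than study drug

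*Combined protocol and SAP*

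**What the plan says.** **The rule.** Section 6 (Risks): "The occurrence of any serious adverse effects will end the patient's participation in the study". The same sentence also halts enrolment while safety is reviewed.

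**Sentences near it.** Two sentences follow directly: "Each and every possible adverse effect of EPO will be investigated and treated individually to minimize the participant's discomfort" and "The safety of having the individual complete the study will also be assessed on an individual basis". The paragraph closes with voluntary withdrawal: "At any time the participant can decide to terminate his participation in the study". Earlier in Section 6 the serious effects are listed: "Serious adverse effects associated with EPO (extremely rare) include anaphylaxis, cerebrovascular accident, deep venous thrombosis", and others. The section opens by saying what the trial adds to usual care: "Completion of the questionnaires and administration of EPO are the only 2 procedures from this protocol" that fall outside standard care.

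**Timing.** Section 2 (Study Procedures) gives dosing as "therapy (preoperative day dosing, dosing 0-2 hours prior to surgery, postoperative day 1 dosing" and follow-up as "completion of efficacy questionnaires at 3, 6, 9 and 12 months postoperatively". The schedule table in Section 2 shows study drug on the pre-operative day, the surgical day and post-operative day 1 only. It shows questionnaires and telephone adverse-event monitoring running to month 12.

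**Primary outcome.** Section 5 (Study Statistics) names the IIEF erectile function domain score at 3, 6, 9 and 12 months. The sample size rests on the 6-month score.

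**The concern.** The rule acts on participation, not on treatment. The paragraph uses the same word for a man who chooses to leave the study, so the natural literal reading is that study procedures stop. After post-operative day 1 no study drug is left to stop. What remains is follow-up, and the IIEF questionnaires are the part of it that usual care would not supply. Nothing in the document says that they continue.

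A man who has a serious effect would then have no later primary-outcome scores because of something that happened after randomisation. The serious effects in Section 6 are described as associated with EPO, so these losses could fall unevenly between arms. The comparison would then no longer cover everyone randomised, and scores that were never collected cannot be recovered.

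**Working it through.** **1. What the rule can stop, by time of event** (dosing and follow-up from Section 2, primary outcome from Section 5)

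| Time of serious effect | Study drug still due | Primary IIEF scores lost, of 4 | 6-month score lost? |
|---|---|---|---|
| After day 1, before month 3 | none | 4 | yes |
| Months 3 to 6 | none | 3 | yes |
| Months 6 to 9 | none | 2 | no |
| Months 9 to 12 | none | 1 | no |

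An event during the dosing days also loses all 4 scores, but there the rule can act on study drug as well.

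**2. The plan's own figure.** Section 5 states 23 per arm for a 5-point difference, one-sided alpha 0.05 and 80% power, with 25 enrolled per arm. No SD is given, so the 23 cannot be checked independently. Solving the two-group t-test (ANOVA with two arms) for the SD that gives 80.0% power at 23 per arm yields 6.71. That SD is back-solved, not stated in the plan.

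**3. Power after losses** (noncentral t, SD 6.71, difference 5)

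| Men with a 6-month score | Power |
|---|---|
| 25 and 25 | 82.9% |
| 24 and 25 | 82.2% |
| 24 and 24 | 81.5% |
| 23 and 23 | 80.0% |

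One loss costs 0.7 percentage points; one loss in each arm costs 1.4.

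**4. Shift in the 6-month difference.** If the lost man would have scored D points below the mean of the other 24 in his arm, leaving him out moves that arm's mean by D/25. D is assumed to lie between 5 and 10.

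- D = 5: 5/25 = 0.2 points, or 0.2/5 = 4% of the target difference.
- D = 10: 10/25 = 0.4 points, or 0.4/5 = 8%.

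The standard error of the difference is 6.71 × √(2/25) = 1.90, so the shift is about 0.1 to 0.2 standard errors. An event after month 6 leaves the 6-month score unaffected.

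**5. How often the rule might be triggered.** The only frequency in the document is that serious EPO effects are extremely rare, so the rates p below are assumptions. The chance of at least one trigger is 1 − (1 − p)^n. The text does not settle whether only effects attributed to EPO count or any serious event does, so both n = 25 and n = 50 are shown.

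| Assumed p per man | n = 50 | n = 25 (EPO arm only) | Expected men among 50 (50p) |
|---|---|---|---|
| 0.1% | 4.9% | 2.5% | 0.05 |
| 0.5% | 22% | 12% | 0.25 |
| 1% | 39% | 22% | 0.5 |
| 2% | 64% | 40% | 1 |

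Because the same rule halts enrolment, 50p is an upper figure if enrolment does not resume.

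**The case against.** **The individual-assessment sentence may already soften the rule.** This stands in part. That sentence can be read to cover serious effects, in which case ending participation is not automatic. But it then conflicts with the flat rule two sentences earlier. If it covers only lesser effects, the flat rule stands. On neither reading does it say that questionnaires continue. A reader might infer that the plan is certain to discard these men's outcomes; the documents support only that it does so if followed literally.

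**Safety follow-up is not clearly lost.** This stands. A reader might infer that adverse-event calls stop and that lost safety contact is the main harm. Section 6 counts only questionnaires and EPO as outside standard care, and says that possible effects of EPO are investigated and treated individually. The triggering event would therefore be followed and usual clinical contact would go on. Whether the scheduled study calls continue is simply not stated. Nor does anything say that scores already collected are thrown away.

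**The efficacy effect is negligible.** It is small, as the figures show, and no strong claim about bias or power can be made. The point rests on principle and on the low cost of the remedy.

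**Keeping post-event scores is a choice of target.** That is fair. After a stroke or myocardial infarction an IIEF score may reflect the event more than nerve recovery, and a sexual-function questionnaire may be unwelcome. But a man can decline, and a collected score can be set aside in a sensitivity analysis, whereas an uncollected one cannot be restored.

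**Conclusion.** The point holds in a limited form. As worded, Section 6 ends participation after a serious adverse effect at times when no study drug remains, and no text keeps the IIEF questionnaires going. Followed literally, it loses 1 to 4 of the 4 primary-outcome scores for the men concerned, after an event that may differ by arm. The status of the scheduled adverse-event calls is unclear.

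The size is small: a shift of about 0.2 to 0.4 points in the 6-month difference for one man lost before month 6, and power of 82.2% with one loss or 81.5% with one loss in each arm. This rests on a back-solved SD of 6.71, an assumed deficit of 5 to 10 points and assumed event rates of 0.1% to 2%. It does not show that the trial's conclusion is at risk. It is a cheap improvement that should be made before an event occurs.

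**What to change.** Reword Section 6 so that a serious adverse effect does not by itself end data collection. State that questionnaires and scheduled adverse-event calls continue to month 12 unless the man withdraws, and that his scores are analysed in the arm to which he was randomised. Reconcile the rule with the individual-assessment sentence, so that the paragraph says plainly what ends and what continues. Leave decisions on study drug, care and the enrolment halt unchanged.

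**Cost.** Protocol wording only: the online or mailed questionnaires and the telephone calls are already in the plan. The downside is minor extra contact with men who had a serious effect, and a few scores affected by that event stay in the primary analysis.

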## **7. Confidentiality**

Paper consent forms, enrollment check sheets, and other source or study documentation will be kept in a study binder. This binder will be stored in a locked office available only to the study team. Electronic data will be housed in a secure password protected REDCap database maintained by the Data Informatics Services Core within the Johns Hopkins Biostatistics Center. Only the study team will have access to this secure database. Of note, to maintain the protected healthy information of patients enrolled in this study, only the study Principal Investigator and primary coordinators will have the ability to export data containing identifying information from this master database. For the purposes of analysis, only de-identified data will be exported.

## **8. Benefits**

The patients' conditions may improve as a result of participation in this study, specifically as related to erectile function. However, there is no guarantee of this. The information from this research study may lead to a better treatment in the future for people with prostate cancer. The patients may not benefit from participation in this study. Their conditions may not get better or may become worse while they are in this study.

## **9. Payment and Remuneration**

There will be no payment or remuneration for the participants in this study.

## **10. Costs**

The cost of the EPO will be covered by the study. There are no other anticipated costs outside of usual care. The participant's insurance, as part of routine care after radical prostatectomy, will be charged for

Date: March 16, 2017

Principal Investigator: [name].

Application Number: IRB00048594

the PDE5 inhibitor drugs such as Viagra, Cialis or Levitra. If the PDE5 inhibitor (Viagra, Cialis or Levitra) is not covered by the participants insurance, they will be responsible for the bill.

Date: March 16, 2017

Principal Investigator: [name].

Application Number: IRB00048594

